# Aim 1: Determine if treatment of MDS/AML with HLA-mismatched CD4+ DLI results in reversal of expression of protein markers of immune exhaustion in recipient cytotoxic T cells.

#### Markers of Immune Exhaustion

Immune exhaustion is characterized by CD8+ T cell surface expression of inhibitory proteins such as PD-1, which contribute to treatment failure in MDS.(14, 36, 76-78) Thus, we wish to assess whether HLA-mismatched CD4+ DLI can reverse expression of negative immune checkpoints on exhausted CD8+ T cells in patients with MDS who failed standard therapy. All enrolled patients will have peripheral blood and bone marrow samples obtained at baseline prior to protocol chemotherapy, and at the time of hematologic recovery, 30-50 days after HLA-mismatched CD4+ DLI. Peripheral blood mononuclear cells (PBMCs) and bone marrow mononuclear cells (BMMCs) will be enriched using standard FicoII-Hypaque methods. The cells will be stained with propidium lodide/acridine orange and live cells will be counted using a Cellometer 2000 automated cell counter (Nexcelom Biosciences, Lawrence, MA). The cells will be suspended in Recovery Freeze Medium (Invitrogen, Carlsbad, CA) and controlled rate frozen to -80°C before transfer to liquid nitrogen storage. In batch, baseline and post-treatment samples will be thawed, followed by isolation of CD4+ and CD8+ populations using MultiSort magnetic MicroBeads (Miltenyi Biotec, Gaithersburg, MD). For this CD4+ cells will be bead captured on one column and the flow through will be mixed with CD8 beads and then captured on a second column. Total RNA will be extracted from one million each of the isolated

\*\*May be obtained earlier than day 42 if ANC recovery to >500/uL. (See study calendar)

CD4+ and CD8+ cells and stored for subsequent RNAseq analysis. The collected samples will be analyzed via multicolor flow cytometric assay to characterize expression of markers of immune exhaustion (TIM3, LAG-3, PD1, PDL1, CTLA4).(79-81) Pre-treatment and post-treatment values will be compared to determine if expression of exhaustion antigens is down regulated after HLA-mismatched CD4+ DLI therapy, thus predicting that immune exhaustion is reversed. The one-sample t-test will be used to assess if the markers are significantly changed after treatment.

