# Aim 2: In patients with MDS/AML who received HLA-mismatched CD4+ DLI therapy, characterize anti-leukemic activity and specificity of recipient marrow CD8+ T cells in response to HLA-mismatched CD4+ DLI.

#### Leukemia-Specific Cytolytic Activity of CD8+ T cells

After treatment with HLA-mismatched CD4+ DLI, we anticipate a reversal of immune exhaustion and a subsequent host-versus-leukemia response. We will evaluate changes to cytolytic activity of the recipient cytotoxic CD8+ T cells before and after therapy, first, in cytotoxicity experiments at different effector:target (CTL:tumor cell) ratios using leukemia blasts collected from the pre-treatment samples. If the frequencies of tumor-reactive T cells required more sensitive methods, we would use ELISPOT testing. Specifically, this sensitive assay can quantify a successful response to HLA-mismatched CD4+ DLI characterized by an increase in the frequencies of CD8+ T cells secreting interferon-γ (IFN-γ) in response to cognate tumor antigen, using peripheral or BM malignant cells as targets.(83) Cytotoxicity and/or ELISPOT results will be compared between patients who achieve a remission and those who do not to show that clinical response is dependent on marrow infiltration by activated cytotoxic T cells. The Satterthwaite ttest will be used to detect a significant difference in changes to cytolytic activity and increase in frequency of CD8+ T-cells before and after treatment, and between patients who achieve a remission and those who do not. The odds ratio will be estimated along with 95% confidence intervals by using the simple logistic regression or the generalized estimating equation (GEE) model. Building multivariable model will not be considered due to the small sample size issue. The data transformation (e.g., log2-transformation) may be considered to meet the normality assumption for the application of parametric analytic tools. The Wilcoxon singed-rank test or Wilcoxon rank-sum test may be considered as the secondary approaches if necessary. As this is an exploratory study, the multiplicity adjustment is not considered.

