# Aim 3: In patients with MDS/AML who received HLA-mismatched CD4+ DLI therapy, characterize cytokine profiles from the blood associated with severe cytokine release syndrome.

#### Plasma Cytokine Profile

HLA-mismatched CD4+ DLI is expected to reverse immune exhaustion and stimulate an inflammatory response consistent with cytokine release syndrome (CRS), characterized by fevers and sometimes associated hypotension or hypoxia.(85) Thus, we aim to identify risk factors for severe CRS in patients treated with this novel therapy. Clinically, we will compare baseline variables of patients who experience severe CRS and those who do not, including HLAmismatched CD4+ DLI dose, degree of HLA mismatch, choice of induction chemotherapy, and disease burden, all factors that are predictive of CRS with other cell therapies. (86-88) In the setting of chimeric antigen receptor T cells (CAR-T) therapy, confirmation that CRS is correlated with high levels of interleukin-6 (IL-6) led to the effective use of IL-6 blockade as CRS treatment.(89-91) We will similarly evaluate cytokine profiles associated with CRS to identify potential targets for anti-CRS therapy. As CRS typically occurs in the first 7 days after other cell therapies, we will collect blood samples prior to therapy and then daily from the day of HLAmismatched CD4+ DLI infusion through day 7 after infusion. We will test plasma using the Ella multiplex cytokine assay to identify the T cell-derived cytokines (e.g., IFN-gamma, IL-6, IL-17, TNF-alpha) increased at baseline in patients who develop severe CRS and monitor which cytokines significantly increase with onset of CRS. For patients who experience CRS, we will also monitor changes to the cytokine profile after administration of IL-6 blockade (tocilizumab) and correlate temporally with clinical resolution. The association between severe CRS and clinical variables (e.g., DLI dose, degree of HLA mismatch, choice of induction chemotherapy, disease burden) and the change of cytokine profiles after treatment (e.g. IFN-gamma, IL-6, IL-17, TNFalpha) will be explored by the Satterthwaite t-test. Specifically, cytokine profiles will be measured at baseline, and days 0 through 7. The GEE model may be employed to assess change over time in the difference between two groups. Odds ratios will be estimated along with 95% confidence intervals by using the simple logistic regression or the GEE model. Other statistical considerations apply as discussed in Aim 2. These studies will confirm whether IL-6 is primarily implicated in causing toxicity with HLA-mismatched CD4+ DLI or if other cytokines may be more effective targets for managing this toxicity.

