
### Power calculations

We expect up to 18 subjects will be enrolled in this phase I with cohort expansion study. For Aim 1, up to 18 subjects will have 80% and 98% power to detect an effect size of 0.7 and 1.0 at a two-sided significance level of 5%. The one-sample t-test is used. For Aim 2 and 3, the maximum power is obtained when the sample size of two groups is identical (i.e., 9 subjects per group). For each endpoint of Aim 2 and 3, the study will have 85% power to detect an effect size of 1.5 at a two-sided significance level of 5% when sample size of each group is 9. If the sample

size of one group deviates from 9, the statistical power will decrease, accordingly. Two sample t-test is used for Aim 2 and 3, and no multiplicity adjustment is considered for power analyses.

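### Aim 3 names a t-test for choice of induction regimen, a nominal factor, and Aim 2 puts its before/after contrast under a two-sample test

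*Combined protocol and SAP*

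**What the plan says.** All the text is in section 8.3.1, Planned Correlative Studies.

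- **Aim 1 (Markers of Immune Exhaustion).** Samples are taken before chemotherapy and at recovery. "The one-sample t-test will be used to assess if the markers are significantly changed after treatment".
- **Aim 2 (Leukemia-Specific Cytolytic Activity).** The test named is Satterthwaite's, which "will be used to detect a significant difference in changes to cytolytic activity and increase in frequency of CD8+ T-cells before and after treatment"; the sentence goes on to add the contrast of remission with no remission. Two contrasts therefore share one test. The text adds: "The Wilcoxon singed-rank test or Wilcoxon rank-sum test may be considered as the secondary approaches if necessary".
- **Aim 3 (Plasma Cytokine Profile).** The association of severe CRS with clinical variables, given as "DLI dose, degree of HLA mismatch, choice of induction chemotherapy, disease burden", and with the change in cytokines, "will be explored by the Satterthwaite t-test". It adds: "Odds ratios will be estimated along with 95% confidence intervals by using the simple logistic regression or the GEE model". An optional GEE covers change over time, and the other Aim 2 considerations carry over.
- **Power calculations.** For up to 18 patients, Aim 1 has 80% and 98% power at effect sizes 0.7 and 1.0. Aims 2 and 3 have 85% power at effect size 1.5 with 9 patients per group. "Two sample t-test is used for Aim 2 and 3".

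Section 6.1.2.2 leaves induction to the treating provider and lists CLAG, 7+3 and HiDAc only as examples.

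**The concern.** The Satterthwaite test is the unequal-variance comparison of two independent means. Two of the uses given to it do not fit.

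First, induction regimen has no mean. With three or more regimens the test runs only after numbers are attached to them, and the p-value then reflects the numbering. The Wilcoxon alternatives carried over from Aim 2 have the same defect for a nominal factor, and no exact or chi-square test is named.

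Second, a before/after comparison in the same patients is paired. Aim 1 recognises this with a one-sample test on changes. Aim 2 has the same pre/post structure, but places that contrast under a two-sample test.

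At stake are an uninterpretable p-value for one CRS risk factor, a possible loss of power for the change in cytolytic activity, and room to choose the test after the data are seen.

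**Working it through.** **1. The plan's own power figures.** Inputs are from the Power calculations text; two-sided 5%, noncentral t.

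- Aim 1, one-sample, n=18, noncentrality d·√18: 79.9% at d=0.7 and 97.9% at d=1.0. The stated 80% and 98% reproduce.
- Aims 2 and 3, 9 v 9, d=1.5, noncentrality 1.5·√(81/18) = 3.18, 16 df: 84.8%. The stated 85% reproduces. A simulated Satterthwaite version gives 84.1%.
- If the calculation had set 18 pre values against 18 post values, d=1.5 would give 99%. The 85% therefore belongs to a contrast between two groups of patients.

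**2. A t-test on regimen.** Illustrative table, not trial data, with 9 severe and 9 non-severe patients to match the plan's 9 v 9:

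| Group | CLAG | 7+3 | HiDAc |
|---|---|---|---|
| A | 2 | 5 | 2 |
| B | 4 | 1 | 4 |

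- Coding CLAG=1, 7+3=2, HiDAc=3: means (2+10+6)/9 = 2.00 and (4+2+12)/9 = 2.00, so p = 1.00.
- Coding CLAG=1, 7+3=3, HiDAc=2: means (2+15+4)/9 = 2.33 and (4+3+8)/9 = 1.67, so p = 0.093.
- The six possible numberings give only these two p-values.
- The Fisher-Freeman-Halton exact test needs no coding: p = 0.28.

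**3. Logistic regression for regimen.** The documents give no severe-CRS rate, so the number of cases is an assumption. Suppose 18 patients and severe CRS unrelated to regimen. An ordinary odds ratio is zero or infinite when some regimen has no cases or only cases. With a 6/6/6 split and 3 cases, the chance is 1 − (6×6×6)/816 = 74%.

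| Severe cases | 6/6/6 split | 10/5/3 split |
|---|---|---|
| 2 | 100% | 100% |
| 3 | 74% | 82% |
| 4 | 47% | 63% |
| 6 | 15% | 37% |

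**4. Before/after in Aim 2, if pre and post were treated as independent samples.** 18 patients, mean shift 0.7 of the marginal SD, two-sided 5%. The pre/post correlation r is not in the documents, so a range is shown. Paired power is the one-sample formula with d = 0.7/√(2(1−r)); the unpaired figures are from simulation with 40,000 replicates.

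| r | Unpaired power | Paired power | True size of unpaired test at nominal 5% |
|---|---|---|---|
| 0 | 53% | 51% | 4.8% |
| 0.3 | 54% | 66% | 2.1% |
| 0.5 | 54% | 80% | 0.8% |
| 0.7 | 56% | 95% | 0.1% |

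At r=0 nothing is lost. At r=0.5 the SD of the change equals the marginal SD, so the paired figure matches the 80% stated for Aim 1.

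**5. Between-group contrasts on change scores.** Remission v no remission, or severe CRS v not, keeps the pairing within each patient's change. Power stays at 84.8% for 9 v 9.

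**The case against.** The strongest reply is that the Aim 2 sentence speaks of a difference in changes and follows one that compares remitters with non-remitters. Read that way, the Satterthwaite test acts on within-patient changes between two patient groups, which is correct. The same reading is natural for cytokine changes in Aim 3. This stands, and it limits the pairing point to the before/after contrast that Aim 2 names alongside the remission contrast.

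Three stronger readings are tempting, and the documents do not support them.

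- *The power section confirms an unpaired before/after test.* It does not: 9 per group out of 18 is a between-patient contrast, and 85% is the figure for that contrast.
- *The plan has no valid method for categorical risk factors or for paired data.* Simple logistic regression takes regimen as a categorical predictor, and the signed-rank test is paired and already listed. Dose level and degree of mismatch can be scored as ordered.
- *The regression models will fail.* That depends on how many severe cases occur, which the documents do not give; zero is possible. The table in the working shows fragility under stated assumptions and does not predict the outcome.

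It is also fair that these analyses are described as exploratory and run as funding permits, and that ignoring positive correlation makes the before/after test conservative. None of this rescues a t-test on regimen.

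**Conclusion.** The point holds in two limited parts.

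- **Aim 3.** The Satterthwaite test as assigned to choice of induction is wrong as written. It has no meaning for three or more regimens unless they are collapsed to two categories, and no exact test is named in its place. This needs no assumption beyond several regimens being used, which section 6.1.2.2 allows.
- **Aim 2.** The before/after contrast is put under a two-sample test while the paired test is only optional, which is inconsistent with Aim 1. The cost is conditional. If an analyst did treat pre and post values as independent, the power lost at a 0.7 SD shift would run from none at r=0 to about 39 points at r=0.7 (95% − 56%).

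Between-group comparisons of change scores and the stated 85% power are sound. The consequence is confined to exploratory correlatives, so this is a wording correction of low severity; the MTD and ORR analyses are untouched.

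**What to change.** In Aim 3, name the Fisher-Freeman-Halton exact test for choice of induction regimen and the rank-sum test for ordered factors such as dose level and degree of HLA mismatch. Keep the Satterthwaite test for cytokine changes between CRS groups. State that Firth or exact logistic regression will be used where ordinary odds ratios separate.

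In Aim 2, split the sentence in two: a one-sample (paired) t-test or signed-rank test for before/after change, and the Satterthwaite test on change scores for remission v no remission. In the power text, say that the 85% refers to the between-group contrast.

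The cost is a few lines of analysis wording and standard software. No added patients, samples or visits are needed.

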# 4.4 END OF STUDY DEFINITION

The phase I portion of the study will continue until reaching the MTD to determine the RP2D. The phase II portion of the study will continue until an additional 10 patients are treated at the RP2D. The maximum total number of patients enrolled in this study will be 28 (6 per dose level plus 10 in the expansion cohort). We expect that the accrual rate will be one patient per every 5-6 weeks. With the DLI observation window (56 days after DLI), the dose-escalation portion may take up to a maximum of 2.5 - 3 years to complete and an additional 1.5 years for the expansion cohort.

A participant is considered to have completed the study if he or she has completed all phases of the study including the last visit or the last scheduled procedure shown in the SOA, Section 1.3.

The end of the study is defined as completion of the last visit or procedure shown in the SOA in the trial globally.

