# 8.3 BIOMARKER, CORRELATIVE, AND SPECIAL STUDIES OR OTHER ENDPOINTS

Specimen Type	Baseline (Pre- treatment)	Days 0-7*	Day 42**
Peripheral blood sample	X	Daily	Х
Bone marrow biopsy/aspirate	Х		Х

\* Research sample collection may be omitted if the day falls on a weekend or holiday.

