#### Management of Cytokine Release Syndrome

CRS Grade	Sign or Symptom	Management
Grade 1	Fever	Symptomatic management of constitutional symptoms and organ toxicities Acetaminophen and hypothermia blanket as needed for fever Assess for infection, empiric broad spectrum antibiotics IV fluids as needed Consider tocilizumab for persistent fever lasting >3 days in patients with significant comorbidities or if patient is deteriorating
Grade 2		
All Grade 2 Cardiac telemetry and pulse oximetry, consider ECHO	Hypotension Not requiring vasopressors	IV fluid bolus of NS 500-1000 mL If patient requires multiple fluids boluses assess fluid balance and consider tocilizumab. For hypotension refractory to fluid boluses: tocilizumab 8 mg/kg IV. For high risk patients consider tocilizumab + dexamethasone 10 mg IV x one  If no response, consider redosing tocilizumab 8 mg/kg IV (may be repeated every 8 h for up to 3 doses in a 24 h period) If hypotension persists after fluids boluses and 1-2 doses of tocilizumab, or if patient is not improving or deteriorating: Consider dexamethasone 10 mg IV every 6 hours. Manage as grade 3 CRS (start vasopressors, transfer to ICU and obtain ECHO) Symptomatic management of constitutional symptoms and organ toxicities
	Hypoxia (Low-flow nasal cannula → O 2 delivered at ≤ 6 L/min)	Supplemental oxygen as needed Tocilizumab 8mg/kg IV For high risk patients consider tocilizumab + dexamethasone 10 mg IV x one If hypoxia persists after above interventions; however oxygen requirement is stable, continue close monitoring. Tocilizumab may be repeated every 8 h for up to 3 doses in a 24 h period If oxygen requirement increases or patient deteriorates: Consider dexamethasone 10 mg IV every 8 hours Manage as Grade 3 CRS Symptomatic management of constitutional symptoms and organ toxicities
Grade 3	Hypotension Requiring one vasopressor +/- vasopressin	IV fluid boluses as needed, vasopressors as needed     Transfer to ICU, obtain ECHO if not performed already     Tocilizumab if not administered previously     Start dexamethasone 10 mg IV every 6 hours if not started previously.     Alternatively methylprednisolone 1 mg/kg IV every 12 hours may be used.     Symptomatic management of constitutional symptoms and organ toxicities

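### Aim 3 allows an uncorrected GEE and ordinary logistic regression to compare probably very few severe-CRS patients with the rest, and does not separate samples taken after rescue treatment

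*Combined protocol and SAP*

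**What the plan says.** Section 8.3.1, Aim 3 (Plasma Cytokine Profile) measures cytokines at baseline and on days 0 through 7, and relates them to severe CRS.

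- The first-named test is the Satterthwaite t-test.
- For the repeated measures, "The GEE model may be employed to assess change over time in the difference between two groups".
- For effect sizes, "Odds ratios will be estimated along with 95% confidence intervals by using the simple logistic regression or the GEE model".
- Aim 2's statistical considerations carry over: Wilcoxon tests as a possible secondary approach, log transformation where needed, no multivariable model because of the small sample, and no multiplicity adjustment because the work is exploratory.
- No working correlation, small-sample variance, penalised or exact logistic method, or minimum number of severe cases is given.

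The Power calculations paragraph says "We expect up to 18 subjects will be enrolled in this phase I with cohort expansion study". For Aims 2 and 3 it notes that "the maximum power is obtained when the sample size of two groups is identical (i.e., 9 subjects per group") and that, with that split, "the study will have 85% power to detect an effect size of 1.5 at a two-sided significance level of 5"%. It adds that power falls with other splits but gives no figure. Section 4.4 sets the maximum enrolment at 28.

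On rescue, Aim 3 plans to follow cytokines after tocilizumab and relate them to clinical resolution. Appendix C includes tocilizumab in the management of grades 2 to 4, and for grade 3 says "Start dexamethasone 10 mg IV every 6 hours if not started previously". Nothing says whether samples drawn after rescue enter the severe versus non-severe comparison. Aim 3 ends by saying the studies will confirm whether IL-6 is the main cause of toxicity or whether other cytokines are better targets.

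**The concern.** The usual GEE sandwich variance is a large-sample result in the number of patients, and here the smaller group governs. Nine samples per patient do not make up for having two or three severe patients. The standard error is then too small and the test rejects too often. Logistic regression has a different weakness: when one group's values all lie above the other's, no finite maximum-likelihood odds ratio exists.

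Rescue treatment adds a problem that no variance correction removes. Tocilizumab blocks the IL-6 receptor, and both it and steroids are given more often as CRS worsens. Later samples in the severe group therefore mix CRS biology with drug effect, and they do so for the very cytokine the aim wants to judge.

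At stake is the claim about which cytokine to target. No dose, DLT or stopping decision depends on it.

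**Working it through.** **Plan's own figure.** Two-sample t-test, two-sided 5%, effect size d = 1.5, groups of 9 and 9. Noncentrality = 1.5 × √(9×9/18) = 1.5 × √4.5 = 3.18 on 16 df, which gives power 84.8%. The stated 85% is reproduced. The same formula for other splits of 18 gives:

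- 2 vs 16: 1.5 × √(32/18) = 2.00, power 47%
- 3 vs 15: 1.5 × √(45/18) = 2.37, power 61%
- 4 vs 14: 1.5 × √(56/18) = 2.65, power 70%
- 5 vs 13: 1.5 × √(65/18) = 2.85, power 76%

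These are pooled-t values. For the Satterthwaite test actually named, simulated power is 32%, 41%, 57% and 68%.

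**How many severe cases?** The documents give no rate, so this is an assumption. If severe means grade 3 or higher (the SAE threshold in Section 8.4.3.3.3, and the grades listed as a DLT in Section 6.1.4), the dose rules limit it. Under Section 9.4.2, taken without the extra accrual that Appendix F permits, an 18-patient escalation allows at most 1 + 1 + 4 = 6 DLTs of any kind. In the expansion, enrolment is held at 2 of 3, 3 of 4-6 or 4 of 7-10 patients (Section 9.4.4). For assumed severe-CRS rates of 10% to 33% among 18 patients, the binomial mean is 1.8 to 5.9 cases, the chance of 2 to 5 cases is 42% to 77%, and the chance of 9 or more is at most about 10%.

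**Behaviour of each method, 18 patients, nominal two-sided 5%.** GEE simulation: nine visits; intercept, time, group and group-by-time; independence working correlation; uncorrected sandwich variance; z reference; normal data with exchangeable correlation 0.5 plus random slopes; 5,000 runs. Figures in brackets come from a separate null simulation. Satterthwaite: 20,000 runs. Logistic: 1,500 runs.

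| Severe cases | GEE group×time, null | GEE 2-df group test, null | Satterthwaite t, null | Logistic Wald, null | Logistic Wald power, d = 1.5 | No finite odds ratio, d = 1.5 |
|---|---|---|---|---|---|---|
| 2 | 27.5% (29%) | 54% | 11.5% | 0% | 0% | 20% |
| 3 | 17.1% (17.5%) | 32% | 6.9% | 0.3% | 2% | 12% |
| 4 | 12.9% (16%) | 23% | 5.7% | 0.5% | 12% | 7% |
| 5 | 11.5% (11%) | 18% | 5.3% | 0.5% | 24% | 6% |
| 9 | 8.4% | 11% | 4.9% | – | – | – |

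AR(1) correlation of 0.6 gives GEE results within about 2 points. Enrolling 28 does not help: group-by-time rejection is 31%, 20%, 14% and 12% with 2 to 5 severe cases. A likelihood-ratio test in the logistic model rejects about 7-8% under the null.

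**Several cytokines.** Aim 3 names four as examples. With four independent tests at 5%, the chance of at least one false positive is 1 − 0.95⁴ = 18.5%, before any inflation.

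**Candidate remedies.**

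- *Bias-reduced sandwich variance*, exchangeable working correlation, 300 runs (Monte Carlo error about 2-4 points): rejection falls from 29% to 18% with 2 severe cases, 14% to 8% with 3, and 15% to 9% with 5. A Mancl-DeRouen variance with a t reference still rejects about 13% with 2.
- *Exact rank test on one summary per patient*: at or below about 5%. It can still reach significance: the smallest two-sided p is 2/C(18,2) = 2/153 = 0.013 with 2 severe cases and 2/C(18,5) = 2/8568 = 0.0002 with 5.
- *Area under the curve cut off at first rescue*: not safe. If all patients share the same rise and fall but severe patients' windows end early, the two groups are compared over unequal windows. With 4-5 severe cases the exact test then rejected about 10-12% in one simulation and 14-16% in another (assumed 2 SD rise peaking on day 3, severe windows ending on days 2-4).

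**The case against.** The case for leaving the plan alone has real content. GEE is optional, and the first-named Satterthwaite test is close to nominal with 4-5 severe cases. Wilcoxon is already a permitted fallback. The work is labelled exploratory and done as funding permits. All of this stands and limits the importance of the point. It does not remove it: the Satterthwaite test is itself off at 2-3 cases, nothing says when the fallback applies, and the closing sentence promises confirmation.

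A reader might also infer stronger things that the documents do not support:

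- **That logistic regression will produce false drivers.** The Wald test errs the other way (0-0.5% false positives). The harm is missing odds ratios and lost power.
- **That rescue occurs only in severe patients.** Appendix C places tocilizumab in grade 2 management, mentions dexamethasone there as an option, and mentions tocilizumab as an option in grade 1. Some rescued patients would be in the comparison group.
- **That the day 0-7 model uses every sample.** Aim 3 does not say so. It is silent, and it describes post-tocilizumab monitoring for a separate purpose. The gap is a missing rule, not a stated analysis.
- **That cytokines will be falsely identified.** The rescue effect has no computed size and could hide a cytokine as easily as implicate one. Aim 3's question about baseline cytokines is not affected by rescue.

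**Conclusion.** The point holds in a limited form. If the optional GEE is used as written, and if 2 to 5 of 18 patients have severe CRS, a nominal 5% group-by-time test has a true error rate of about 29% down to 11%. The Satterthwaite test is inflated mainly at 2 and 3 cases, at about 11% and 7%. Ordinary logistic regression leaves no finite odds ratio in about 20% down to 6% of data sets at a 1.5 SD shift, which is a loss of information and not a source of false positives. Post-rescue samples, more frequent in severe cases but not confined to them, have no stated place in or out of the group comparison.

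The case count is an assumption supported by the DLT rules, not a figure in the protocol. The error rates rest on simulated normal data and change little with the correlation structure tried. A method that holds its level is available at almost no cost, so this is worth changing even in an exploratory aim.

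**What to change.** In Section 8.3.1, Aim 3:

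1. Make the primary cytokine comparison an exact rank-sum or permutation test on one value per patient: log change from baseline, from pre-rescue samples, over a window of the same length in both groups, for example the mean of fixed early days. Do not use an area under the curve truncated at rescue.
2. Fix the window before the data are seen, with rules for a patient rescued inside it and for missing days. Section 8.3 says "Research sample collection may be omitted if the day falls on a weekend or holiday", and infusions run from Tuesday to Saturday, so the days lost differ between patients (days 4 and 5 after a Tuesday infusion, days 1 and 2 after a Friday one).
3. Define severe CRS for this aim, and report post-rescue values separately.
4. If GEE is kept, use a bias-corrected variance with a t reference, and treat its results as descriptive when there are only about 2-3 severe cases.
5. Use Firth-penalised or exact logistic regression for odds ratios.
6. Say that the studies explore, rather than confirm, the role of IL-6.

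The cost is revised wording, slightly more analysis work and fewer nominally significant results. No extra patients or samples are needed.
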